11.4. Social Responsiveness Scale, Second Edition

The SRSTM-2 identifies the presence and severity of social impairment within the autism spectrum and differentiates it from that which occurs in other disorders. It is a 65-item, parent-

completed questionnaire which incorporates 5 content areas of social deficits: social awareness, social cognition, social communication, social motivation, and autistic mannerisms. The SRSTM-2 should be administered as described in Table 3, is estimated to take about 15-20 minutes to complete, and will be proctored by the local rater. (Appendix 5) (Constantino et al. 2003; Constantino and Gruber 2005).

12. ASSESSMENTS OF SAFETY

12.1. Safety Parameters

12.1.1. Demographic/Medical History

A complete demographic and medical history will be obtained at Screening. Medical history will be updated on Day 0, prior to dosing on Day 1, to confirm trial eligibility. Any confirmed DSM-5 diagnoses (American Psychiatric Association 2013) should be documented.

12.1.2. Vital Signs

Vital signs will include blood pressure (systolic and diastolic), heart rate, respiratory rate, and temperature and will be performed after the subject has been at rest in the seated position for at least 5 minutes. Vital signs will be assessed at the Screening Visit and as clinically indicated per Table 3.

12.1.3. Physical Examinations

A complete physical examination will be performed at the Screening Visit, Day 0, Day 42, Day 91/ET Visit, and End of Trial Visit, and will include an assessment of the following body systems: height (at the Screening Visit only); general appearance; weight; mental status; head, eyes, ears, nose, and throat; dermatologic; cardiovascular; respiratory; gastrointestinal; musculoskeletal; and neurological at Screening. Additional body systems may be examined at the Investigator's discretion. An abbreviated, clinically focused physical examination based on the Investigator's clinical judgement will be administered at all other assessment intervals or as clinically indicated. Any clinically significant abnormality should be reported on the AE CRF page, as appropriate.

12.1.4. Electrocardiograms

A 12-lead ECG in triplicate will be obtained at the at the Screening Visit, Day 0, Day 42, Day 91/ET Visit, and End of Trial Visit, with the subject in a supine position following at least a 5-minute rest. The Investigator will review and report the results of each ECG; the reviews on Days 42 and 91 will include a comparison of each ECG to the baseline (i.e., Day 0) ECG. Any clinically significant abnormality should be reported as an AE, as appropriate.

12.1.5. Laboratory Assessments

The clinical laboratory tests (chemistry, hematology, and urinalysis) that will be performed are shown in Table 5. Samples will be obtained at the Screening visit, Day 0, Day 42, Day 91/ET Visit, and End of Trial Visit.

| Chemistry | Hematology | Urinalysis | |
|----------------------------|---------------------------------|---|--|
| Alkaline phosphatase | Hemoglobin | Glucose | |
| Aspartate aminotransferase | Hematocrit | Protein | |
| Alanine aminotransferase | Mean corpuscular hemoglobin | Specific gravity | |
| Total bilirubin | Mean corpuscular hemoglobin | pH | |
| Total protein | concentration | Nitrite | |
| Albumin | Mean corpuscular volume | Bilirubin | |
| Glucose | Erythrocyte count | Urobilinogen | |
| Carbon dioxide | Leukocyte count | Ketone | |
| Blood urea nitrogen | Neutrophil count and percentage | Blood | |
| Creatinine | Lymphocyte count and | Leukocyte esterase | |
| Sodium | percentage | Other | |
| Potassium | Monocyte count and percentage | | |
| Chloride | Eosinophil count and percentage | eGFR (at Screening only; using | |
| Calcium | Basophil count and percentage | the revised Schwartz equation; Fadrowski and Furth 2011, | |
| | Platelet count | Staples et al. 2010) | |

Table 5:Clinical Laboratory Tests

eGFR = estimated glomerular filtration rate

Other laboratory tests will include serum and urine pregnancy tests (β-human chorionic gonadotropin) in females of childbearing potential, and urine drug tests (amphetamines/methamphetamines, benzodiazepines, cannabinoids, cocaine, opiates).

A sample will be collected at Screening for centralized 22q11DS genotype testing to confirm diagnostic homogeneity of the trial population. Results of this test will not be required prior to randomization of each subject as historical or local records confirming diagnosis will be adequate to establish trial eligibility.

Reports containing these laboratory test results will be generated by the laboratory performing the test. Laboratory values outside of the normal range will be assessed for clinical significance by the Investigator.

Abnormal laboratory tests may be repeated at the discretion of the Investigator or Sponsor.

Other laboratory tests may be performed by the Investigator, as deemed necessary, to evaluate, or ensure the safety of, a subject. The performance of special testing (i.e., other than the protocol-defined testing) that the Investigator deems necessary should be discussed in advance with the Medical Monitor, if the subject's clinical status allows.

A blood sample to assess serum proline levels will be collected as described in Table 3. There is evidence that proline affects glutamatergic neurotransmission. PRODH, a protein coding gene, encodes the enzyme proline dehydrogenase, which is involved in the transformation of the amino-acid proline into pyrroline-5-carboxylate, which in turn is the precursor of glutamate. In a subset of patients with 22q11DS, plasma proline levels are found to be increased (Goodman et al. 2000). Variability in proline levels in 22q11DS is likely related to polymorphisms in the remaining allele of the PRODH gene (Bender et al. 2005). In 22q11DS, several studies indicate a

possible relation between high proline and changes in neuropsychiatric phenotypes (Raux et al. 2007; Vorstman et al. 2009; Magnee et al. 2011) but this observation is not consistently replicated (Evers et al. 2015).

If any blood remains from the sample collected for centralized confirmation of 22q11DS genotype, the remnant blood samples will be stored per the federal (and/or local) regulations that govern the laboratory's processes on biological sample (and laboratory report) retention. Additionally, if a new protocol and informed consent form are developed to investigate the remnant samples, these documents will be submitted for IRB and/or EC approval and the subject and/or parent/guardian will be required to provide documented informed consent for additional analyses of the samples. Table 3. At the time of signing the initial ICF for this trial, NB-001-01, the subject and/or parent/guardian will have the option to decline future research on any remnant blood sample.

Blood samples for PK analysis and 4β -hydroxycholesterol will be collected at the timepoints noted in Table 3.

12.1.6. Columbia–Suicide Severity Rating Scale

Consistent with Food and Drug Administration (FDA) Guidance, Guidance for Industry Suicidal Ideation and Behavior: Prospective Assessment of Occurrence in Clinical Trials, (FDA 2012), the C-SSRS is used to evaluate SIB. The scale consists of 10 categories with binary responses (yes/no) to assess the subject's suicidal thoughts. An additional question regarding self-injurious behavior without suicidal intent will be evaluated with a binary response (yes/no). The overall suicidal ideation score is a composite endpoint based on categories of suicidal ideation, suicidal behavior, and SIB. The C-SSRS will be used at the visits noted in Table 3 to evaluate the subject's suicidal tendencies. Subjects with suicidal tendencies at Screening (or Day 0, if more than 21 days elapse between Screening and Day 1), based on Investigator assessment, will be excluded according to the Exclusion Criteria (Section 7.2). Investigator guidelines for managing a subject with SIB will be provided separately (Posner et al. 2011).

The C-SSRS is provided in Appendix 6 and administration of the C-SSRS is expected to take 15 to 20 minutes.

12.2. Adverse and Serious Adverse Events

12.2.1. Definition of Adverse Events

12.2.1.1. Adverse Event

An AE is defined as any untoward medical occurrence in a clinical investigation subject administered an IP and which does not necessarily have a causal relationship with the product. An AE can therefore be any unfavorable and unintended sign (including an abnormal laboratory finding), symptom, or disease temporally associated with the use of a pharmaceutical product, whether or not it is considered related to the pharmaceutical product.

Pre-existing events that increase in frequency or severity in nature during or as a consequence of use of an IP will also be considered as AEs. Any medical condition or clinically significant laboratory abnormality with an onset date before the date of ICF signature is pre-existing and

should be documented as medical history. Any AE that occurs between the date of ICF signature and the date/time of first IP administration will be considered a pre-treatment-emergent AE. Any AE that occurs after the date/time of first IP administration will be considered a TEAE.

Often, a clinically significant laboratory value is an abnormal laboratory value that is accompanied by a sign or symptom. Typically, a diagnosis or set of clinical signs and symptoms including abnormal laboratory value(s) is captured as the AE term (e.g., anemia). However, in the absence of a diagnosis, a clinically significant laboratory abnormality may be captured as an AE term (e.g., elevated alanine aminotransferase). All laboratory values, including abnormal values, will be reported during the trial.

12.2.1.2. Serious Adverse Event

An AE is considered serious if it results in any of the following outcomes or circumstances:

- Death
- Life-threatening
 - The term life threatening in the definition of "serious" refers to an event in which the subject was at immediate risk of death at the time of the event. It does not refer to an event, which hypothetically might have caused death, if it were more severe.
- Inpatient hospitalization or prolongation of existing hospitalization
 - Hospitalization for elective intervention for a pre-existing condition that did not worsen from baseline is not considered an AE.
- Persistent or significant disability/incapacity
 - The term disability means a substantial disruption of a person's ability to conduct normal life functions.
- Congenital anomaly/birth defect in the offspring of a subject

Medical and scientific judgement should be exercised in deciding whether expedited reporting is appropriate in other situations. Important medical events that may not result in death, be immediately life-threatening, or require hospitalization may be considered serious adverse events (SAEs) when, based upon appropriate medical judgment, they jeopardize the subject and require medical or surgical intervention to prevent one of the outcomes listed in this definition.

Definition of Terms

Life-threatening: An AE is life-threatening if it places the subject at immediate risk of death from the event as it occurred (i.e., it does not include an event that, had it occurred in a more severe form, might have caused death). For example, drug induced hepatitis that resolved without evidence of hepatic failure would not be considered life threatening, even though drug induced hepatitis can be fatal.

Hospitalization: An AE requiring hospitalization should be considered an SAE. Hospitalization scheduled for an elective procedure or treatment of a pre-existing condition that has not worsened during participation in the trial (e.g., elective surgery for a pre-existing condition that

has not worsened), or for a routine clinical procedure that is not the result of an AE is not considered an SAE. If anything untoward is reported during the procedure, that occurrence must be reported as an AE, either serious or non-serious, according to the defined criteria. In general, hospitalization signifies that the subject has been detained (usually involving at least an overnight stay) at the hospital or in the emergency department for observation and/or treatment that would not have been appropriate in the physician's office or outpatient setting.

Disability/incapacity: An AE is disabling or incapacitating if the event results in a substantial disruption of a subject's ability to conduct normal life functions.

12.2.1.2.1. Reporting Serious Adverse Events

Any AE that is assessed as serious, whether or not it is related to the IP, must be reported by the Investigator to the Medical Monitor within 24 hours of knowledge of the event and documented on the SAE CRF. An initial SAE CRF should be completed with the available information, even if additional information will be needed to fully document the event. All additional information relevant to the SAE must be provided to the Medical Monitor as soon as possible. Relevant medical records, including, as applicable, hospital records and autopsy reports, should be obtained by the Investigator and provided to the Medical Monitor.

In the event of a fatal or life-threatening SAE, any required information for the initial report must be provided and expedited to the Medical Monitor to allow for regulatory reporting by the Sponsor within 7 calendar days of the Investigator's initial report.

The Investigator will follow an SAE until it resolves, the Investigator feels the event is stable and chronic in nature, or the subject is lost to follow-up. All follow-up information relevant to the SAE must be provided to the Medical Monitor within 24 hours of the Investigator's receipt of this information.

SAEs will be reported from the time of signing the ICF and, if applicable, the subject assent form, and through the End of Trial Visit.

SAEs should be reported on the SAE CRF in the EDC system:

12.2.1.3. Treatment-Emergent Adverse Event of Special Interest

A treatment-emergent adverse event of special interest (TEAE-SI) is an AE of scientific and medical concern specific to the Sponsor's study drug/device or program, which may warrant ongoing monitoring and/or rapid communication by the investigator to the sponsor or designee. Such an event might warrant further investigation in order to characterize and understand it.

TEAEs-SI in this trial will include: development of psychotic symptoms, SIB, seizure, overdose with untoward medical sequalae, and confirmed cases of COVID-19. Such events will require expedited reporting to the Sponsor within 24 hours of knowledge of the event.

12.2.2. Overdose

Any instance of overdose (suspected or confirmed, accidental or intentional, with or without untoward sequelae, and irrespective of whether or not the IP was involved) must be reported by the Investigator to the Medical Monitor by telephone or email within 24 hours of knowledge of the event. An overdose with no associated signs or symptoms will not be classified as an AE or SAE but should be reported to the Medical Monitor. Any signs or symptoms of overdose should be documented as an AE or SAE (as applicable); an overdose associated with an SAE should be reported according to the SAE reporting procedures.

In the case of an overdose, the subject will be monitored closely and managed with supportive care. Any symptoms will be treated according to the Investigator's standard practices.

12.2.3. Pregnancy

If a female subject becomes pregnant at any time following the first dose of IP through the End of Trial Visit, the Investigator must notify the Medical Monitor within 24 hours of learning of the pregnancy by completing the Pregnancy CRF in the EDC system. IP will be discontinued, and the subject will be withdrawn from the trial. Female subjects will be instructed to report a pregnancy that occurs within 90 days of the End of Trial Visit. The Investigator must report the pregnancy to the Medical Monitor within 24 hours or as soon as possible after learning of it. Any premature terminations of pregnancy, including elective/therapeutic and/or spontaneous abortions, must be reported to the Medical Monitor. Each pregnancy will be followed to its conclusion. For pre-term or term deliveries, the status of the mother and child after delivery must be reported to the Medical Monitor by updating the Pregnancy CRF in the EDC system. Although pregnancy occurring in a clinical trial is not considered to be an AE or SAE, any pregnancy complication will be recorded as an AE or SAE and will be followed as such. A spontaneous abortion (i.e., miscarriage), a medically-recommended therapeutic abortion, and an ectopic pregnancy will always be reported as an SAE. In the event of a pregnancy-associated AE or SAE, the AE or SAE should be reported by adding the appropriate event term(s) to the AE CRF in the EDC system.

12.2.4. Relationship to Investigational Product

After careful medical consideration, the Investigator will assess the relationship of the AE to the IP according to the following categories:

- Not related: A causal relationship between IP and the AE can be easily ruled out (e.g., based on the temporal relationship, absence of a reasonable pathophysiologic mechanism, or direct evidence of actual cause). An alternate etiology must be documented in the source record.
- Related: An AE that is most likely caused by the IP, per Investigator assessment. Rechallenge is not required to fulfill this definition.

If no valid reason exists for suggesting a relationship, then the AE should be classified as "not related." If there is any valid reason, even if undetermined, for suspecting a possible cause-and-effect relationship between the IP and the occurrence of the AE, then the AE should be considered "related" to IP.

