5.2. Endpoints

5.2.1. Primary Endpoint

• Type, frequency, severity, and causality of TEAEs, treatment-emergent serious adverse events (TESAEs), clinically significant changes from baseline in: laboratory tests, electrocardiograms (ECGs), vital signs, and physical examination findings during treatment with NB-001

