- Subject incidence of TEAEs by relationship to IP, MedDRA system organ class, and preferred term;
- Subject incidence of the most frequently-occurring TEAEs related to IP (i.e., related TEAEs occurring in ≥ 10% of the SAF) by MedDRA preferred term;
- Subject incidence of ≥ Grade 3 TEAEs related to IP by MedDRA system organ class and preferred term;
- Subject incidence of SAEs by MedDRA system organ class and preferred term;
- Subject incidence of serious TEAEs by CTCAE grade, MedDRA system organ class, and preferred term; and
- Subject incidence of serious TEAEs by relationship to IP, MedDRA system organ class, and preferred term.

In addition, subject incidence of TEAEs by system organ class and preferred term will be summarized by treatment sequence for the washout and follow-up periods.

At each level of summarization (e.g., any AE, system organ class, and preferred term), subjects experiencing more than one TEAE will be counted only once. In the summary of TEAEs by CTCAE grade, subjects will be counted once at the highest grade reported at each level of summarization; in the summary of TEAEs by relationship, subjects will be counted once at the closest relationship to IP. Adverse event data will be presented in data listings by subject, treatment sequence, treatment group, and event.

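### Protocol 12.2.4 defines neither causality category to cover a merely possible drug reaction, and does not say that the lower threshold in its next paragraph governs

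*Protocol*

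**What the plan says.** Protocol 12.2.4 asks the investigator to place each AE in one of two categories.

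- 'Not related': "A causal relationship between IP and the AE can be easily ruled out". The bullet adds: "An alternate etiology must be documented in the source record".
- "Related: An AE that is most likely caused by the IP, per Investigator assessment". The bullet treats this as a definition to be met: "Rechallenge is not required to fulfill this definition".

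The paragraph after the bullets gives a second pair of rules. With no valid reason to suggest a relationship, the event is not related. The event is related "If there is any valid reason, even if undetermined, for suspecting a possible cause-and-effect relationship between the IP and the occurrence of the AE".

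Protocol 5.2.1 includes causality in the primary endpoint: "Type, frequency, severity, and causality of TEAEs". SAP 4.5.2 plans four outputs that use the rating:

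- "Subject incidence of TEAEs by relationship to IP, MedDRA system organ class, and preferred term"
- related TEAEs occurring in at least 10% of the safety set
- related TEAEs of Grade 3 or higher
- serious TEAEs by relationship

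In the relationship summaries each subject counts once, at the closest relationship. The SAP does not define 'related'. Footnote p to Protocol Table 3 reserves the relationship rating to the investigator.

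**The concern.** The bullets set a high bar at each end and leave the middle undefined. The paragraph sets a single lower bar that covers everything. The two are not worded as one rule, and neither document says which prevails.

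The middle is where judgment is hardest. An example is somnolence or irritability in week 2 with no clear other cause. An investigator guided by the 'Related' bullet would hesitate to call it most likely drug-caused. With only one other option, that investigator might record it as not related. A colleague guided by the paragraph would record it as related.

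Safety is the primary objective, 3 to 5 centers are planned, and no data monitoring committee is planned (Protocol 15.7). At stake is whether a named component of the primary endpoint means the same thing at every site, and whether possible reactions are under-recorded.

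**Working it through.** The documents give no causality split and no figure to reproduce, so the check is one of logic. The inputs are the two bullets and the following paragraph of Protocol 12.2.4. Every AE falls into one of four types.

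| Type of event | By the bullets | By the paragraph |
|---|---|---|
| 1. Most likely due to the IP | Related | Related |
| 2. Possible, but not most likely | Neither definition met | Related |
| 3. Not easily excluded, but no valid reason to suspect the IP | Neither definition met | Not related |
| 4. Easily excluded, other cause documented | Not related | Not related |

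Three things follow.

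- The bullets are not exhaustive: types 2 and 3 have no category.
- The paragraph is exhaustive, since a valid reason either exists or does not.
- No type is expressly related under one rule and not related under the other. The difference lies between no category and a category.

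Type 2 is the case that matters for the related-TEAE tables. Type 3 raises a smaller point. The paragraph makes the event not related, but the 'Not related' bullet demands a documented alternate etiology, and there may be none to document.

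To show how sensitive the SAP tables are, assume that the safety set holds between 30 subjects (the planned evaluable number) and 34 (the approximate number randomized), and that all of them contribute to the treatment group in question. SAP 4.5.2 reports subject incidence, so the unit is one subject whose closest relationship changes.

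- One subject: 1/34 = 2.9 percentage points; 1/30 = 3.3 points.
- The 10% cut-off at 34 subjects: 3/34 = 8.8% falls below it and 4/34 = 11.8% above.
- The 10% cut-off at 30 subjects: 2/30 = 6.7% falls below it and 3/30 = 10.0% meets it.

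At either size, one changed rating can decide whether a preferred term enters the table of frequent related TEAEs. How many subjects would change cannot be derived from the documents.

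**The case against.** The strongest reply is that the section, read as a whole, already resolves the case. The bullets describe two categories and the paragraph says how to choose between them. It leans toward related whenever a valid reason exists, even an undetermined one. On that reading nothing is left unassigned, and an investigator who ignores the sentence is misapplying the protocol.

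Much of this stands. It also rules out some stronger inferences that a reader might draw:

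- **That two sites could rate the same event in opposite ways and both comply.** The documents do not support this. A possible event fails the 'Not related' bullet as well as the 'Related' one, so the bullets never permit not related for it. The only text that assigns it says related.
- **That the paragraph waives the alternate etiology.** It is silent on the matter, and the bullet's requirement can stand beside it.
- **That the related rate could swing by the whole fraction of in-between events.** Any such fraction would be assumed. The calculation would also count every in-between event as not related under the bullets, which they do not allow, and a fraction of events does not translate into subject incidence.

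The consequences are bounded too. Subjects, investigators, raters and the sponsor are blinded (Protocol 9.4), and each subject is planned to receive both treatments, so one investigator's reading need not favor either. SAEs go to the Medical Monitor regardless of relationship (Protocol 12.2.1.2.1), and overall TEAE incidence does not use the rating.

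The reply does not remove the mismatch itself. The paragraph is not labelled as the governing rule. The 'Related' bullet presents itself as a definition to be met, and its bar is plainly higher than a possible relationship. Balance between treatments also does not protect the absolute related-TEAE rates.

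**Conclusion.** The concern holds as an unreconciled definition with a foreseeable route to error. Protocol 12.2.4 uses two thresholds for related, its category definitions omit events that are only possible reactions, and neither document says which text governs. An investigator who applies the higher wording could under-record possible reactions as not related. The four relationship outputs and the causality component of the primary endpoint would then depend on the sentence used.

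The likely direction is toward too few related events; the size is unknown. The per-subject figures above rest on an assumed safety set of 30 to 34 and show sensitivity only; they do not predict an effect. The CRF completion guide is not among the documents and may already address the point. Efficacy analyses and sample size are not touched. This merits correction because it is cheap and concerns the primary endpoint, but it does not threaten the safety conclusions as a whole.

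**What to change.** Reconcile Protocol 12.2.4 to one exhaustive threshold.

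- Reword the 'Related' bullet to the section's own closing rule: any valid reason to suspect a possible causal relationship.
- Reword 'Not related' as its exact complement: no valid reason to suspect one.
- Keep the source-record requirement, but as a documentation step separate from the category definition. Record the alternate etiology where one is identified; otherwise record why no relationship is suspected. Simply replacing the bullet would drop this requirement.
- Repeat the definition in SAP 4.5.2 and in the CRF completion guide.

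The cost is a short wording change in two documents and the guide. Somewhat more events may be coded as related on both NB-001 and placebo. If ratings have already been made, say in the study report which wording was in force when they were made.
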